20.5.2 Open-Label Extension Period

All efficacy endpoints for the Open Label Extension will be summarized by descriptive statistics, no inferential statistical analysis will be performed.

All “change from baseline” and “mean slope decline” types of endpoints will be summarized with descriptive statistics (number of observations, mean, standard deviation, median,

minimum, and maximum) for numerical (or continuous) variables and with frequencies and percentages for categorical variables at each visit. Box Whisker and trend plots maybe used to present the data if necessary.

All “time to event” type endpoint will be summarized descriptively (n, mean, standard deviation, minimum, Q1, median, Q3, maximum, and 95% CI) for each treatment group. Kaplan-Meier curve will be plotted to present the data.

The statistical analysis plan will describe in further detail the analyses for primary, secondary, efficacy endpoints.

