
Study Title: A Multicenter, Double Blind, Placebo Controlled Study to Assess the Efficacy and Safety of H.P. Acthar® Gel in the Treatment of Subjects With Amyotrophic Lateral Sclerosis

Protocol Number: MNK14042068

Type: Phase 2b

Condition/Disease:

Amyotrophic Lateral Sclerosis

[REDACTED]

Open Label Extension

All efficacy endpoints for the Open Label Extension will be summarized by descriptive statistics only, no inferential statistical analysis will be performed.

All “change from baseline” and “mean slope decline” types of endpoints will be summarized with descriptive statistics (number of observations, mean, standard deviation, median, minimum, and maximum) for numerical (or continuous) variables and with frequencies and percentages for categorical variables at each visit. Box Whisker and trend plots maybe used to present the data if necessary.

All “time to event” type endpoint will be summarized descriptively (n, mean, standard deviation, minimum, Q1, median, Q3, maximum, and 95% CI) for each treatment group. Kaplan-Meier curve will be plotted to present the data.

[REDACTED]

Safety

[figure not shown]
Treatment-emergent adverse events and serious adverse events will be summarized using the appropriate version of MedDRA by preferred term within system organ class. Other safety data will be listed and summarized descriptively or graphically, as appropriate.

[REDACTED]

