10.2 Secondary Objectives

The secondary objectives of this study are:

- To assess the safety and tolerability of Acthar in subjects with ALS.
- To assess the effect of Acthar on survival in subjects with ALS.
- To assess longitudinal effect of Acthar on functional decline in subjects with ALS
- To assess the longitudinal effect of Acthar on survival in subjects with ALS

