20 STATISTICAL METHODS AND PLANNED ANALYSIS

20.1 General Considerations

This section provides a general description of the statistical methods to be used in analyzing both safety and efficacy data. The key statistical issues or considerations will be addressed. A more detailed statistical analysis plan will be provided in a separate document that will be finalized prior to interim analysis.

Unless otherwise specified, all statistical tests will be two-sided with a significance level of 0.05. Summary statistics will be provided for all study variables with descriptive statistics (number of observations, mean, standard deviation, median, minimum, and maximum) for numerical (or continuous) variables. Frequency and percentages will be calculated for categorical variables. Data summary and analyses will be performed with SAS 9.2 or higher.

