20.10 Statistical Power and Sample Size Considerations

The primary efficacy analysis will compare the mean telephone administered ALSFRS-R total score change from baseline at Week 36 in the group treated with Acthar to that in the placebo group using mITT analysis population. With 140 mITT subjects in the group treated with Acthar and 70 mITT subjects in the placebo group (210 subjects total), assuming the expected ALSFRS-R total score change from baseline of 6.3 and 9 in Acthar and placebo groups, respectively, the common SD of the ALSFRS-R total score change from baseline at Week 36 of 5.83 (estimated from PRO-ACT database), and dropout rate of 20% prior to Week 36, the study will have at least 80% power to detect the treatment difference at the 0.05 level of significance. Assuming a few subjects might not qualify for the mITT analysis population after randomization, approximately 213 subjects will be enrolled and randomized into Acthar treated group and placebo group in a 2:1 ratio.

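### Extension decline is tabulated visit by visit with no slope derivation or handling of death and dropout, so selective attrition could make decline after Week 36 look about 8-19% slower with no drug effect

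*Combined protocol and SAP*

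**What the plan says.** Section 20.5.2 limits extension efficacy to description: "All efficacy endpoints for the Open Label Extension will be summarized by descriptive statistics, no inferential statistical analysis will be performed". The Synopsis gives the same rule for the change-from-baseline and mean-slope endpoints: these "types of endpoints will be summarized with descriptive statistics (number of observations, mean, standard deviation, median, minimum, and maximum"), at each visit. Time-to-event endpoints get descriptive statistics and a Kaplan-Meier curve.

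Section 20.3.3 lists the extension endpoints by sequence group (Acthar-Acthar and placebo-Acthar): telephone ALSFRS-R change and mean slope, mean slopes of FVC, FEV1 and SVC, and survival. No section says how an extension slope is computed. None says how a subject who has died or left enters the functional summaries. Section 20.11.1 leaves imputation to a separate SAP, and Section 20.11.2 commits sensitivity analyses for the primary endpoint only.

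Entry to the extension (Section 12.1.1) requires completing 36 weeks and an investigator's opinion that the subject will benefit. One secondary objective that these data can inform is "To assess longitudinal effect of Acthar on functional decline in subjects with ALS" (Section 10.2).

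**The concern.** ALS is fatal, and Section 16.1 describes the ALSFRS-R as predicting survival. Subjects who lose points fastest are therefore likely to die or stop first. Those rated at Weeks 60 to 84 would then be the slower progressors, and the curve of visit means would flatten even if every individual kept declining at a constant rate.

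Part of that flattening falls after Week 36, when placebo subjects start Acthar. Section 20.3.3 presents the extension endpoints group by group, so a reader will naturally compare each group before and after the switch. A slowing produced by attrition could then be taken for a drug effect in the placebo-Acthar group, or for a sustained effect in the Acthar-Acthar group.

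**Working it through.** **1. The plan's own figure.** Inputs from Section 20.10: "With 140 mITT subjects in the group treated with Acthar and 70 mITT subjects in the placebo group (210 subjects total"), an "expected ALSFRS-R total score change from baseline of 6.3 and 9 in Acthar and placebo groups, respectively", a PRO-ACT-based SD of 5.83 for that change, and 20% dropout before Week 36. Section 20.1 adds that "all statistical tests will be two-sided with a significance level of 0.05".

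- Completers: 0.8 × 140 = 112 and 0.8 × 70 = 56.
- Standard error: 5.83 × √(1/112 + 1/56) = 0.954.
- 2.7/0.954 = 2.83. Power = Φ(2.83 − 1.96) = 80.8% (80.3% with the t distribution).

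This agrees with the statement that "the study will have at least 80% power to detect the treatment difference at the 0.05 level of significance". The design effect is 2.7/9 = 30%, a difference between arms at Week 36.

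**2. Inputs for the attrition check, with no drug effect.**

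- Mean slope: 36 weeks is 36/4.345 = 8.285 months, and 9/8.285 = 1.09 points/month.
- Slope SD 0.62 points/month with residual SD 2 per visit (assumed split): √[(0.62 × 8.285)² + 2 × 2²] = √(26.4 + 8) = 5.86, close to the plan's 5.83.
- Attrition: 20% by Week 36 is the plan's figure. The same hazard continued (assumption) gives 1 − 0.8^(84/36) = 41% by Week 84, or 1 − 0.8^(48/36) = 26% of entrants.
- Hazard of leaving multiplied by e^0.5, e^1.0 or e^1.5 (1.6 to 4.5) per extra point/month (assumption).

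**3. Visit means of those rated.** Simulation of 400,000 subjects, negative slopes set to zero, true mean slope 1.099. The slope before Week 36 is the mean change at Week 36 divided by 8.285 months. The slope after is the rise in mean change from Week 36 to Week 84 divided by 48/4.345 = 11.05 months.

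| Hazard ratio per point/month | Before Week 36 | After Week 36 | Apparent slowing |
|---|---|---|---|
| 1.6 | 1.057 | 0.968 | 1 − 0.968/1.057 = 8% |
| 2.7 | 1.020 | 0.867 | 1 − 0.867/1.020 = 15% |
| 4.5 | 0.987 | 0.808 | 1 − 0.808/0.987 = 18% |

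Without the floor at zero the range is 9% to 19%. With no link between leaving and decline it is about 0%. A second simulation, with leaving driven by the decline seen so far (hazard ratio 1.35 to 2.0 per SD) and several splits of the variance between slope and residual, gave about 7% to 20%.

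**4. Other estimators on data of the second kind, decline after Week 36 against entrants' true decline.**

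- Visit means: 8% to 20% too slow.
- Average of each subject's own regression slope after Week 36: from 0.9% too slow to 5.5% too fast.
- Model with random intercept only, as in Section 20.5.1: 5% to 14% too slow.
- Model with random intercept and random slope: within 0.1%.

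When leaving depends on the underlying slope, as in step 3, missing-at-random holds only approximately. The random-slope model then fell short by 1 − 1.087/1.112 = 2%, 1 − 1.061/1.103 = 4% and 1 − 1.029/1.087 = 5%. On the sparser investigator-administered schedule it gave nearly equal slopes before and after Week 36, within roughly 1% to 5% of truth. Some of those fits raised convergence warnings, so the near-equality of the two slopes is the result to rely on. FVC was not simulated.

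**The case against.** The strongest reply is that the plan is openly descriptive and not finished. Section 20.5.2 defers detail to the SAP, which is not available here, and no test or decision depends on the extension. That stands, and it limits the point to a request for specification. Four stronger readings are tempting, and the documents do not support them.

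- *Visit means of survivors are the only output.* Section 20.3.3 also lists a mean-slope endpoint and survival, and n is reported at each visit. Subject-level regression slopes would remove most of the bias. The gap is that the derivation is unstated. Restriction to those still rated is itself an inference: Section 15.4.1 confines telephone follow-up after early termination to the Randomized Treatment Period, while Section 22.1 has no such limit.
- *The bias is 12-26%, close to the 30% the trial is sized on.* Those percentages compare the slope after Week 36 with the true population slope (1 − 0.968/1.099 = 12%; 1 − 0.808/1.099 = 26%), which no reader of the display sees. The means before Week 36 are flattened too. The 30% is also a between-arm effect, whereas this is a before-after artefact within each group.
- *The extension is the sole source for the longitudinal objective.* Section 10.2 does not say so, and the slope and over-time endpoints of Section 20.3.2 also serve it.
- *Carrying the Section 20.5.1 slope model forward would be enough.* That model names a random intercept only.

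**Conclusion.** The point holds as a modest, inexpensive improvement. As written, the extension summaries could show each group's ALSFRS-R decline slowing by about 8% to 19% after Week 36 with no drug effect.

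The size rests on two assumptions outside the documents: about 40% lost by Week 84, and a hazard of leaving that rises 1.6- to 4.5-fold per extra point per month. The direction is supported by the protocol's own view of the scale as prognostic, but the strength of the link is unknown, and with no link the bias is about zero. Attrition could also be heavier: in the pilot study 13 + 7 = 20 of 43 subjects (47%) completed Week 36 (Sections 9.1 and 9.4), although other doses were included.

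The artefact partly cancels in a comparison of the two sequence groups and leaves the primary analysis untouched.

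**What to change.** In Section 20.5.2, or in the SAP paragraph it points to:

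- Derive the extension slope endpoints (ALSFRS-R and FVC) from a mixed model with random intercept and random slope. Fit it to Weeks 0-84, with separate slopes for Weeks 0-36 and 36-84 by randomized group and 95% confidence intervals, labelled descriptive. State which subjects contribute; using all mITT subjects keeps those who left before Week 36.
- For the ALSFRS-R, use the investigator-administered version, which is scheduled at Weeks 0, 12, 24 and 36 and at each extension visit. Table 7-2 schedules no telephone ALSFRS-R.
- Reconcile Section 20.3.3 with the schedule. It names the telephone ALSFRS-R and an SVC slope, but Table 7-2 lists only FVC and FEV1, and Section 16.5 collects SVC at Baseline only.
- Show cumulative deaths and dropouts beside n in every visit table and plot.

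The cost is a paragraph of text and one extra model. The model relies on linear decline within each period and on data missing at random. Both should be stated beside the estimates.

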15.4 Dosing Procedures

Both Acthar (80 U/mL) and the placebo are supplied as 5 mL multidose vials. The vials should not be over pressurized prior to withdrawing the product. The vials should be warmed to room temperature before using and will be labeled according to all applicable national and local regulations.

The following treatments will be administered:

Randomized Treatment Period

- Treatment A: Acthar 0.2 mL (16 U) SC QD for 36 weeks. Subjects who do not enter the open label extension will then taper with Acthar 0.2 mL (16 U) administered 2x/week for 2 weeks, then 1x/week for 1 week.

OR

- Treatment B: Placebo 0.2 mL SC QD for 36 weeks. Subjects who do not enter the open label extension will then taper with placebo 0.2 mL administered 2x/week for 2 weeks, then 1x/week for 1 week.

Open Label Extension:

- Acthar 0.2 mL (16 U) SC QD for 48 weeks, followed by Acthar 0.2 mL (16 U) administered 2x/week for 2 weeks, then 1x/week for 1 week.

The subject or subject's caregiver will administer the first dose of study drug and the first dose of Acthar in the Open Label Extension in the clinic under the supervision of study staff. The subject will remain in the clinic for at least 1 hour postdose to monitor for allergic or anaphylactic reactions. All other doses will be administered by the subject or the subject's caregiver at home.

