20.3.3 Secondary Efficacy Endpoints-Open Label Extension Period

- Change from baseline in telephone administered ALSFRS-R over time in the group treated with Acthar followed by Acthar (Acthar-Acthar) and the group treated with placebo followed by Acthar (placebo-Acthar).
- Mean slope of telephone administered ALSFRS-R total score decline from baseline in Acthar-Acthar and placebo-Acthar groups.
- Mean slope of pulmonary function test (FVC, FEV1, and SVC) decline in Acthar-Acthar and placebo-Acthar groups.
- Survival in Acthar-Acthar and placebo-Acthar groups.

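### Open-label survival is to be tabulated with mean, SD, minimum and maximum, which do not summarise heavily censored data validly; the quartiles and 95% CI are not tied to Kaplan-Meier

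*Combined protocol and SAP*

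**What the plan says.** Section 20.3.3 lists "Survival in Acthar-Acthar and placebo-Acthar groups" as a secondary efficacy endpoint of the extension, and Section 10.2 makes the longitudinal effect on survival a secondary objective.

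Section 20.5.2 says time-to-event endpoints will be "summarized descriptively (n, mean, standard deviation, minimum, Q1, median, Q3, maximum, and 95% CI) for each treatment group". The Synopsis has the same list: "summarized descriptively (n, mean, standard deviation, minimum, Q1, median, Q3, maximum, and 95% CI". In both places the next sentence adds a graph: "Kaplan-Meier curve will be plotted to present the data".

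Extension efficacy endpoints are to be "summarized by descriptive statistics, no inferential statistical analysis will be performed". Section 20.5.2 closes by deferring detail: "The statistical analysis plan will describe in further detail the analyses for primary, secondary, efficacy endpoints". Section 20.1 says that plan is a separate document; it is not among the documents reviewed here.

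For these endpoints the visible text gives no time origin, no censoring rule, no count of events and censored subjects, and no statement of how the quartiles are estimated or what the 95% CI refers to.

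**The concern.** The list reads like a summary of a fully observed continuous variable. The paragraph before it in Section 20.5.2 prescribes number of observations, mean, SD, median, minimum and maximum for change scores. All six reappear in the time-to-event list, with Q1, Q3 and a 95% CI added.

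Survival times in the extension will not be fully observed. Anyone alive at the end of follow-up, or lost before it, contributes only a lower bound. A simple mean must then either leave those subjects out or treat their last contact as if it were a death. SD, minimum and maximum have the same difficulty and are not standard Kaplan-Meier outputs.

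This table is the only numerical survival summary specified in the visible text for the extension. Because nothing is tested there, the tabulated values and the curve are the whole result, and the two could give different impressions of the same data.

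**Working it through.** The documents give no event count, survival rate or power for this endpoint, so there is no stated figure to reproduce. The calculations below are illustrations; they show how the listed statistics behave if computed simply on observed times.

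**Follow-up.** Section 15.4 gives the randomized period ("Acthar 0.2 mL (16 U) SC QD for 36 weeks") and the extension ("Acthar 0.2 mL (16 U) SC QD for 48 weeks"). Time from extension entry is therefore limited to 48 weeks, and time from Week 0 to 36 + 48 = 84 weeks. The plan does not say which origin applies.

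**A. Events-only mean, two assumed hazards.** Take exponential survival with hazards 0.15 and 0.30 per year (assumed), C = 48 weeks, a 52-week year and no dropout.

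- Survival: S = exp(-hC). At 0.15, hC = 0.1385 and S = 0.8707. At 0.30, hC = 0.2769 and S = 0.7581.
- Mean of all observed times: (1 - S)/h = 44.8 and 41.9 weeks.
- Mean among deaths: [(1 - S)/h - C·S]/(1 - S) = 23.4 and 22.9 weeks.

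Survival differs by 11 percentage points (87% versus 76%). The events-only mean differs by half a week, because it mainly reflects the length of the window.

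**B. Censoring and dropout.** Section 9.1 cites 70% to 80% mortality within 5 years of symptom onset, and Section 20.10 assumes 20% dropout before Week 36. Treating both as constant rates (an assumption) gives:

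- death hazard λ = -ln(1 - p)/260 = 0.00463 per week (p = 0.70) or 0.00619 (p = 0.80);
- dropout rate μ = -ln(0.80)/36 = 0.00620 per week, or 0;
- h = λ + μ; proportion censored = 1 - (λ/h)(1 - exp(-hT));
- restricted mean = (1 - exp(-λT))/λ; mean of all observed times = (1 - exp(-hT))/h;
- events-only mean = 1/h - T·exp(-hT)/(1 - exp(-hT)).

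| p | T (weeks) | Dropout | Censored | True survival at T | Restricted mean | Mean of all observed times | Events-only mean |
|---|---|---|---|---|---|---|---|
| 0.70 | 48 | none | 80% | 0.80 | 43.0 | 43.0 | 23.1 |
| 0.70 | 48 | 20% per 36 weeks | 83% | 0.80 | 43.0 | 37.4 | 21.9 |
| 0.80 | 48 | none | 74% | 0.74 | 41.5 | 41.5 | 22.8 |
| 0.80 | 48 | 20% per 36 weeks | 78% | 0.74 | 41.5 | 36.2 | 21.6 |
| 0.70 | 84 | none | 68% | 0.68 | 69.6 | 69.6 | 39.3 |
| 0.70 | 84 | 20% per 36 weeks | 74% | 0.68 | 69.6 | 55.2 | 35.7 |
| 0.80 | 84 | none | 60% | 0.60 | 65.5 | 65.5 | 38.4 |
| 0.80 | 84 | 20% per 36 weeks | 68% | 0.60 | 65.5 | 52.2 | 34.8 |

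Between 60% and 83% are censored. Without dropout, the mean of all observed times equals the restricted mean. With dropout it falls short by 43.0 - 37.4 = 5.6 or 41.5 - 36.2 = 5.3 weeks at T = 48, and by 14.4 or 13.3 weeks at T = 84. At T = 48 the mortality contrast itself moves the restricted mean by only 43.0 - 41.5 = 1.5 weeks. Unequal dropout could therefore outweigh or reverse it. In an extreme case, the lower-mortality group with dropout shows 37.4 weeks and the higher-mortality group without dropout shows 41.5.

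**C. Median.** The true median is ln 2/λ = 150 or 112 weeks, beyond either horizon, so a Kaplan-Meier median would normally be reported as not reached. A simple median of all observed times would be 48 weeks at T = 48, and 56 to 84 weeks at T = 84.

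**The case against.** The strongest reply is that the plan never says these are simple statistics of observed times. Q1, median, Q3 and a 95% CI are usual Kaplan-Meier outputs, and a Kaplan-Meier curve is promised in the very next sentence. A reader might infer that the plan ignores censoring altogether. The documents do not support that: the method of calculation is unstated, and the curve handles censoring. What remains is that the quantiles and CI are not tied to the estimator, and that mean, SD, minimum and maximum are prescribed whatever is meant by the rest.

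A reader might also infer that the table could not show a mortality difference at all. That goes too far. With censoring only at 48 weeks, the mean of all observed times (44.8 versus 41.9 weeks in A) is the restricted mean, a legitimate quantity that moves in the right direction. Nor is it fair to compare these figures with an unrestricted mean survival, which no nonparametric method can estimate from 48 weeks of follow-up. The objection to the all-subjects mean rests on dropout, and on the absence of a stated horizon.

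The analysis is also descriptive: everyone in the extension receives active drug, and no test or primary conclusion depends on the table. Some of the missing counts will appear elsewhere, since deaths are summarised with serious adverse events (Section 20.7.1) and discontinuation reasons are tabulated (Section 20.4.4). All of this stands and limits the consequence.

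Finally, detail is deferred to the separate statistical analysis plan, and text just before Section 20.5.2 is blacked out. A censoring convention may exist there. That does not make the four listed statistics suitable, and carrying the present list forward would carry the problem with it.

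**Conclusion.** The point holds as a defect in the prescribed table. Mean, SD, minimum and maximum are listed for an endpoint likely to be mostly censored, and the text does not identify the quartiles and 95% CI as Kaplan-Meier estimates. Computed simply, an events-only mean is almost insensitive to mortality (about 23 weeks under either of two hazards differing two-fold), and an all-subjects mean is pulled down by dropout (5 to 6 weeks at a 48-week horizon, 13 to 14 weeks at 84).

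These sizes depend on constant hazards. The 5-year mortality runs from symptom onset, and extension entrants are a selected group who completed 36 weeks (Section 12.1.1). The dropout figure is stated only up to Week 36 and is extended beyond it here. The exact values are therefore uncertain; heavy censoring is the robust part.

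The documents do not establish that censoring will be ignored or that a survival difference would be hidden from a reader who also sees the curve. The consequence is confined to the tabulated secondary survival results of the extension. It is worth correcting, but does not affect the primary conclusion.

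**What to change.** In Section 20.5.2 and in the Synopsis, for time-to-event endpoints:

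- Remove mean, SD, minimum and maximum, or replace the mean with a restricted mean at a stated horizon.
- Report the numbers of subjects, events and censored observations in each group.
- State that Q1, median, Q3 and their 95% CIs are Kaplan-Meier estimates, shown where reached.
- Tabulate Kaplan-Meier survival with 95% CI at fixed study weeks, for example Weeks 48, 60, 72 and 84.
- State the time origin (Week 0 or extension entry) and the censoring rule. The origin matters because extension entrants must have completed 36 weeks, so a curve for them starting at Week 0 would be flat up to entry by construction.

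Carry the same wording into the separate statistical analysis plan. The cost is a sentence or two in each place and a standard table shell.
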